For time to event endpoints, the log rank test stratified by baseline lung function (FVC <50% vs. 50% to 75% vs. >75% predicted) will be used to compare the time to event endpoints between the two treatment arms. Time will be measured relative to the date of randomization (Day 1). Patients who do not experience the event will have their data censored on the last date during the placebo-controlled period when, on the basis of the assessments in accordance with this protocol, the patient can be considered to have been event-free. Any patients who undergo lung transplantation will be censored at the date of the transplant. Sensitivity analyses will be provided with lung transplant counted as an event for PFS and time from randomization to death or non-elective hospitalization from any cause.

The primary efficacy assessments for the randomized placebo-controlled period are made on the study day of initiation of the open-label lebrikizumab through Week 52. Assessment on this day will be included for analyses of the randomized placebo-controlled period, but subsequent assessment during the open-label period or after Week 52 will be excluded.

The hazard ratio and its 95% CI will be estimated with the use of a Cox regression model stratified by baseline lung function. In fitting the Cox model, ties will be handled with the approximate likelihood method of Efron (1977). Kaplan-Meier curves will be provided.

Summary statistics of the *ATAQ-IPR* and *SGRQ* endpoints and the changes from baseline will be calculated at each assessment time-point for each treatment group. The mean, standard error, and median of the absolute scores and the mean changes from baseline (and 95% CIs) between treatment groups will be reported for the endpoint. For scores involving change from baseline, patients without baseline values will be excluded from the analyses. Line charts depicting the means and mean changes of subscales over time will be also provided. Scoring for the questionnaire will be based on relevant user manuals.

Frequencies and percentages of missing data for the *ATAQ-IPR* and *SGRQ* endpoints will be compared between the two treatment arms.

Additional details for summarization, sensitivity analyses, and type I error control are provided in the SAP.

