4.4.1 Type I Error Control Plan

The fixed-sequence testing procedure ([Westfall and Krishen, 2001](#)) will be used to control the overall type I error rate for statistical testing of the primary and key secondary efficacy endpoints.

Contingent upon statistical significance in the primary efficacy endpoint—annualized rate of decrease in percentage of predicted FVC over 52 weeks, the key secondary endpoints will be tested at a two-sided significance level of 5% in the order as shown below:

- Time from randomization to death from any cause
- Annualized rate of decrease in percentage of predicted DL_{CO} over 52 weeks
- Time from randomization to first respiratory-related hospitalization
- Time from randomization to first acute exacerbation or death from any cause
- Annualized rate of change in the ATAQ-IPF total score over 52 weeks
- Annualized rate of decrease in 6MWT distance over 52 weeks
- Time from randomization to first occurrence of a $\geq 15\%$ absolute decrease in percentage of predicted DL_{CO} or death from any cause
- Time from randomization to first occurrence of a $\geq 10\%$ absolute decrease in percentage of predicted FVC or death from any cause
- PFS defined as time to all-cause death, all-cause hospitalization or $\geq 10\%$ relative decrease in FVC (L), whichever occurs first

If a test is not significant at 0.05 level, then the subsequent test(s) will not be considered significant regardless of the associated p-value(s).

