4.4.3 Secondary Efficacy Endpoints

Time-to-Event Endpoints

The log rank test stratified by baseline lung function ($\text{FVC} < 50\%$ vs. 50% to 75% vs. $> 75\%$ predicted) will be used to compare the time to event endpoints between two treatment arms. The hazard ratio and its 95% CI will be estimated using a Cox regression model

stratified by baseline lung function. In fitting the Cox model, ties will be handled with the approximate likelihood method of Efron (1977). Kaplan-Meier plots will be provided.

Time-to-event will be measured in reference to the date of randomization. The primary efficacy assessments for the randomized placebo-controlled period are made on through the Week 52 visit, assessment on this day will be included for analyses of the randomized placebo-controlled period, but subsequent assessment during the open-label period or after Week 52 will be excluded. Patients are considered to be in the placebo controlled period even if they have discontinued study treatment if they would still be receiving placebo controlled study treatment had they not discontinued. For time to non-elective hospitalization or death from any cause, time to first event of acute IPF exacerbation, time from randomization to death from any cause, and time to respiratory hospitalization, patients not experiencing an event will be censored at the earlier of last known alive day, study day 368 or the last date during the placebo-controlled period.

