For time to first occurrence of a $\geq 10\%$ absolute decrease in percentage of predicted FVC or death from any cause, time to PFS, time to first occurrence of a $\geq 15\%$ decrease in percentage of predicted DL_{CO} or death from any cause, and time to first SGRQ Total Score ≥ 7 or death from any cause, deaths which occur within 168 days after the last clinic assessment and before the week 52 visit (and before start of open label treatment) will be counted as events. For the PFS analysis, hospitalization will be counted as events following the same rule as for death. Patients without an event will be censored at the last clinic assessment during the placebo controlled period. Any patients who undergo lung transplantation will be censored at the date of the transplant. Sensitivity analyses will be provided with lung transplant counted as an event for PFS and time from randomization to death or non-elective hospitalization from any cause. For the sensitivity analyses, only lung transplant, death, or non-elective hospitalization which occur within 168 days after the last clinic assessment and before the week 52 visit (and before start of open label treatment) will be counted as events.

Annualized Rate of Decrease Endpoints

The annualized rate of decrease in FVC (mL/year) will be analyzed and summarized with use of the same method as for the annualized rate of decrease in percentage of predicted FVC. Diffusing capacity, 6MWT distance, and the ATAQ-IPF score will also be analyzed and summarized with the same methods. For the annualized rate of decrease in FVC (mL/year) height, sex, and age will be included in the model as covariates.

Categorical summaries will be provided with categories of decrease of ≥ 50 meters or death before the visit, decrease of 50 to >0 meters, and stability or improvement of ≥ 0 meters for the 6MWT distance; summaries will be provided with categories of decrease of $> 15\%$ or death before visit, decrease of 15% to $>0\%$, stability or improvement of $\geq 0\%$ for percentage of predicted DL_{CO}.

Rules for missing ATAQ-IPF V3 and SGRQ data are described in Section 4.8.

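### The lung-transplant sensitivity rule in SAP 4.4.3 matches the main analysis of neither endpoint it covers: the hospitalization type differs for PFS, and the 168-day limit is new for death or non-elective hospitalization

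*Combined protocol and SAP*

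**What the plan says.** The relevant text is in SAP 4.4.3, under the time-to-event endpoints.

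- **Transplant in the main analyses.** "Any patients who undergo lung transplantation will be censored at the date of the transplant".
- **What the sensitivity analyses are.** "Sensitivity analyses will be provided with lung transplant counted as an event for PFS and time from randomization to death or non-elective hospitalization". Protocol 6.4.2 asks for the same thing ("Sensitivity analyses will be provided with lung transplant counted as an event for PFS", and likewise for the second endpoint) and adds no further event rule.
- **The event rule for those sensitivity analyses.** One sentence covers both endpoints together and restricts what counts by type and by time: "For the sensitivity analyses, only lung transplant, death, or non-elective hospitalization which occur within 168 days after the last clinic assessment". Countable events must also precede Week 52 and any open-label dosing.
- **Main rule for PFS.** Deaths count if they fall within 168 days of the last clinic assessment and before Week 52. Then: "For the PFS analysis, hospitalization will be counted as events following the same rule as for death". No type of admission is excluded. SAP 4.4.1 agrees ("PFS defined as time to all-cause death, all-cause hospitalization or" a relative FVC decrease of at least 10%), as does the outcome list in SAP 2.2.2.
- **Main rule for death or non-elective hospitalization.** This endpoint belongs to a different group: "For time to non-elective hospitalization or death from any cause, time to first event of acute IPF exacerbation", all-cause death and respiratory hospitalization. For these, "patients not experiencing an event will be censored at the earlier of last known alive day, study day 368" or the last date of the placebo-controlled period. No 168-day limit is set.

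SAP section 1 states that the SAP takes precedence over the protocol, so the SAP sentence governs.

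**The concern.** The main analyses censor a patient at transplant. In IPF that censoring may be informative, and the sensitivity analysis is there to show whether the result depends on it. It can do so only if transplant handling is the one thing that differs from the main analysis.

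The shared sentence breaks this for both endpoints. If a sensitivity hazard ratio differed from the main one, the reader could not tell whether the cause was transplant, the type of hospitalization (PFS), or the event window (death or non-elective hospitalization). If the two agreed, that agreement could hide opposing changes. Two programmers could also derive different event sets from the same data, one following the definition of the analysis and the other the sentence after it.

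**Working it through.** The plan states no figure on this point to reproduce. The check sets the rules side by side and applies them to days taken from the schedule of assessments.

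| Feature | PFS, main | PFS, sensitivity | Death or non-elective hosp., main | Death or non-elective hosp., sensitivity |
|---|---|---|---|---|
| Transplant | censored | event | censored | event |
| Hospitalization counted | all-cause | non-elective named | non-elective | non-elective |
| 168-day limit | yes | yes | **no** | **yes** |
| Latest day | before Week 52 | before Week 52 | up to Day 368 or end of placebo-controlled period | before Week 52 |

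The first row is the intended change. For PFS the second row also changes. For the other endpoint the third row changes, and the fourth changes slightly.

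**PFS, example.** Last clinic assessment Day 169, elective admission Day 200. The gap is 200 − 169 = 31 days, inside the 168-day window, and Day 200 is before Week 52. The main analysis has an event on Day 200. The sensitivity rule does not name this admission, so the patient stays at risk.

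**Death or non-elective hospitalization, example.** The last day counted under the sensitivity rule is the last clinic day + 168, if that comes before Week 52:

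- Day 29: 29 + 168 = Day 197
- Day 85: 85 + 168 = Day 253
- Day 169: 169 + 168 = Day 337
- Day 197: 197 + 168 = Day 365, the scheduled Week 52 visit

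Take a last clinic assessment on Day 85 and a death on Day 300. The gap is 300 − 85 = 215 days, more than 168, so the sensitivity analysis does not count it. Day 300 is before Day 368, so the main analysis does.

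**Who can be affected by the limit.** It closes before Week 52 only for patients last assessed before Day 365 − 168 = Day 197 (Week 28). A patient who stops drug and completes safety follow-up has a last clinic visit 126 days after the last dose. If that visit is the last clinic assessment, the window closes at last dose day + 126 + 168 = last dose day + 294. This falls before Day 365 only if the last dose was before Day 71, that is on Day 1, 29 or 57, giving closing days 295, 323 and 351. The group is small, and an event must also become known to the study after the patient's visits have ended.

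**The case against.** The strongest case is that this is loose drafting with almost no consequence.

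*The sentence may be meant only as a time window.* It follows the main PFS rule and repeats its 168 days. That reading is plausible, but the sentence still names non-elective admissions for PFS and still gives the second endpoint a limit that its main analysis lacks. Protocol 6.4.2, which lacks the sentence, does not resolve this, because the SAP takes precedence.

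*A reader might infer that the PFS sensitivity analysis drops the FVC component altogether*, since the sentence admits only transplant, death and non-elective hospitalization. The documents do not support that. The preceding sentence defines the analysis as PFS with transplant added, and a limit on time since the last clinic assessment has no work to do for an FVC decline, which is measured at an assessment.

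*Few patients meet the 168-day condition.* This stands. Patients who stop drug are asked to continue visits or enter safety follow-up, those who refuse follow-up are asked to attend an early termination visit, and nobody is followed after withdrawing consent (protocol 3.1.1, 4.5.17.3, 4.6.1.1 and 4.6.1.2). A late known death such as the Day 300 example is possible but should be uncommon.

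*Transplants should also be few*, because patients expecting one within 12 months are excluded (protocol 4.1.2). This limits the stakes, but it also means the effect under study is small and easily obscured by a second change.

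**Conclusion.** Both mismatches are in the current SAP text and do not depend on any assumed rate. The sensitivity rule changes the hospitalization component for PFS and the event window for death or non-elective hospitalization, so neither analysis isolates the transplant censoring rule.

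The impact is minor. The analyses are supportive and untested. PFS is last of the nine key secondary endpoints in SAP 4.4.1, and death or non-elective hospitalization is outside that sequence. The primary endpoint and all main results are unaffected.

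Two stronger conclusions should not be drawn. A reader might put a number or a direction on the distortion. The documents give no rate for elective admissions, transplants or PFS events. They also do not say whether the admission for a transplant already counts as an all-cause hospitalization in the main PFS analysis; if it does, adding transplant as an event may change little. A reader might also conclude from the non-elective wording remaining in protocol 3.2.4 that the main PFS definition is unsettled. It is not: SAP 2.2.2, 4.4.1 and the main rule in 4.4.3 agree, and the SAP governs.

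**What to change.** Before Cohort B is unblinded, replace the shared sentence in SAP 4.4.3 with text such as:

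> Each lung-transplant sensitivity analysis uses the same events, counting windows and censoring as the main analysis of its endpoint, with one change: lung transplant is an event rather than a reason for censoring. PFS therefore keeps death, all-cause hospitalization and a relative FVC decrease of at least 10%, with the 168-day rule. Death or non-elective hospitalization keeps its main censoring rule, without a 168-day limit.

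Add one line saying whether an admission for the transplant itself is handled as transplant or as hospitalization, in the main and the sensitivity analyses alike.

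No new data are needed and no main definition changes. The cost is in Cohort A, which has already been analysed: check how its transplant sensitivity analyses were programmed, and rerun them if they used the shared sentence. The SAP version in force at that analysis is not among the documents, so this cannot be settled from the text.

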4.4.4 Exploratory Efficacy Endpoints

Time-to-Event Endpoints

These endpoints will be analyzed and summarized with use of the same methods for the time-to-event secondary endpoints.

Change-from-Baseline Endpoints

These endpoints will be analyzed and summarized with use of the same methods as the endpoint—change from baseline in percentage of predicted FVC in Section 4.4.2.

Annualized Rate of Decrease Endpoints

The annualized rate of decrease in SpO₂ (%) over 52 weeks will be analyzed and summarized with use of the same method as for the annualized rate of decrease in percentage of predicted FVC.

4.4.5 Sensitivity Analyses

The following additional sensitivity analyses will be performed:

- A. A Rank ANCOVA analysis of change from baseline to week 52 in percentage of predicted FVC stratified by baseline lung function (FVC < 50% vs. 50% to 75% vs. > 75% predicted) will be performed with death ranked as worst according to time until death (patient with the shortest survival time will be assigned the worst rank) and other missing results imputed the last observation carried forward method. These analyses will be performed as described in [Stokes et al. 2000](#).
- B. The annualized rate of decrease in *percentage of* predicted FVC over 52 weeks and the annualized rate of decrease in percentage of predicted DL_{CO} over 52 weeks will be performed using the random slope model with missing due to death imputed with the worst value observed in the study during the randomized treatment period, through week 52, among any Cohort A patient. Other missing data will be implicitly imputed by the model based on an individual's estimated rate of worsening of lung function prior to study visit discontinuation (i.e., assuming missing at random).
- C. The annualized rate of *decrease in percentage of* predicted FVC over 52 weeks will be performed using the random slope model with missing data imputed with the multiple imputation method only from placebo patients. The multiple imputation method will be implemented with the following specifications.
 1. 100 imputation datasets will be created separately from steps a and b
 - a) The MCMC method will be used for partial imputation of non-monotone missingness, only to produce a monotone missing pattern. The seed will be 5815733.
 - b) The monotone method will then be used with regression method. The baseline lung function (FVC < 50% vs. 50% to 75% vs. > 75% predicted), treatment group, and all prior visits will be included in the model to impute the following visit. The seed will be 8246205

2. The random slope analysis will be performed for each imputation dataset and the results will be combined following the methodology developed by Rubin (1978, 1987).
- D. The absolute change from baseline to Week 52 in percent (%) predicted FVC and the absolute change from baseline to Week 52 in percentage of predicted DL_{CO} will be performed using the MMRM model with missing due to death imputed with the worst value observed in the study during the randomized treatment period, through Week 52, among any Cohort A patient. Other missing data will be implicitly imputed by the model (i.e. assuming missing at random).

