4.4.2 Primary Efficacy Endpoint

The primary endpoint is annualized rate of decrease in percentage of predicted FVC through Week 52, which will be compared across treatment arms with use of a random slope model on observed cases at a 0.05 two-sided significance level.

The statistical model is as follows:

$$FVC_{ijk} = (\beta_0 + \beta_{0k}) + (\alpha_i * \beta_1 + \beta_{1k}) * t_k + \eta_k + \epsilon_{ijk}$$

where FVC_{ijk} is the predicted FVC for kth patient at visit j in treatment group i; β_0 is the intercept; α_i and β_1 is the interaction term of the treatment effect ($i = \text{lebri or placebo}$) and the slope; t_k is assessment time (continuous in year) for patient k; η_k is the effect of baseline lung function (defined as $FVC < 50\%$ vs. 50% to 75% vs. $> 75\%$ predicted) for the kth patient; β_{0k} and β_{1k} are the random components for intercept and slope; ϵ_{ijk} is the random error for kth patient at time j; β_{0k} , β_{1k} , and ϵ_{ijk} are assumed to be independent and normally distributed with mean 0 and variance of σ_0^2 , σ_1^2 , and σ_ϵ^2 respectively.

Of note, because of a relatively large number of strata defined by the randomization stratification factors, the analysis will be adjusted for baseline lung function only because baseline FVC may impact the clinical disease course.

From the model, least squares means for the annualized rate of decrease in each treatment arm and the difference between the two treatment arms will be provided with

95% CIs. The model implicitly imputes missing data based on an individual's estimated rate of worsening of lung function prior to study visit discontinuation (i.e., assuming missing at random).

There are several different approaches to summarizing the treatment effect which are ways of understanding the results rather than independent endpoints. For summarizing treatment effect the following will be provided but not considered as separate endpoints or hypotheses.

- Change from baseline to landmark visit time expressed as absolute and relative difference
- Difference in annual rate of decrease expressed as absolute and relative difference
- Categorical absolute change from baseline to each visit time with categories of decrease of $\geq 10\%$ or death before the visit, decrease of 10% to $>0\%$, stability or improvement of change $\geq 0\%$

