4.8 MISSING DATA

Missing data will be handled as specified in the analysis method Section 4.4.

Missing individual items for the scoring of the SGRQ will be handled as follows: The symptoms component will be considered missing if more than two of the items are missing. The activity component will be considered missing if more than four of the items are missing. The impacts component will be considered missing if more than six of the items are missing. The total score will be considered missing if any component is missing. For a valid component questionnaire with unanswered questions, the predefined weight and score for a particular missing question will be used to calculate the aggregated score for the component (St George's Respiratory Questionnaire Manual, Version 2.3). Missing data will not be imputed.

Missing individual items for the scoring of the ATAQ-IPF will be handled as follows. If more than half of the items in a domain have responses, then scores for missing items may be imputed using the mean score from non-missing items. If half or more items are missing, then the domain is not scored.

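### Sensitivity analysis C is described as placebo-based, but its imputation step includes treatment group and names no fitting population; fitted to both arms, it only repeats the missing-at-random assumption

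*Combined protocol and SAP*

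**What the plan says.** SAP 4.4.5, item C, repeats the random slope analysis of the annualized rate with "missing data imputed with the multiple imputation method only from placebo patients". It continues: "The multiple imputation method will be implemented with the following specifications". Two steps follow.

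- Step a: "The MCMC method will be used for partial imputation of non-monotone missingness, only to produce a monotone missing pattern". No arm or reference group is named.
- Step b: a monotone regression in which baseline lung function, "treatment group, and all prior visits will be included in the model to impute the following visit". No fitting population is named here either.

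The number of imputations (100), both seeds and the combining rules are fixed. SAP 4.8 adds only this: "Missing data will be handled as specified in the analysis method Section 4.4". The Version 2 amendment rationale lists one change to multiple imputation, the reduction from 1000 to 100 datasets. Protocol 6.4.2 leaves sensitivity analyses to the SAP.

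**The concern.** The lead sentence shows that placebo-based imputation is intended. The steps that are meant to implement it do not carry this out, and one listed predictor makes sense only under a different analysis. If step b is run on both arms, the treatment coefficient carries the lebrikizumab effect into the imputed values.

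This matters because of what the other sensitivity analyses cover. Items B and D change the assumption for deaths only and keep missing at random for everyone else. Item A departs from it for living dropouts, with "other missing results imputed the last observation carried forward method", but on change at Week 52 rather than on the slope. Item C is therefore the only check, on the primary annualized rate, of what happens if living dropouts do not continue along their own arm's course. Fitted to both arms, it would return the primary result under a placebo-based label.

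**Working it through.** **The two readings.** Write the step b regression for visit j as: mean of Y(j) = a + b × (lung function and prior visits) + τ(j) × treatment.

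- *Fitted to placebo patients only.* Treatment is constant. With an intercept, the seven earlier visits (Weeks 0 to 44) and treatment, the Week 52 design has 9 columns but rank 8. No τ can be estimated, so the term is inert.
- *Fitted to both arms.* τ(j) is estimated and added to every imputed lebrikizumab value. Missing values then follow the patient's own arm given the observed history. That is missing at random, as SAP 4.4.2 states for the primary model.

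**Inputs from the documents.** SAP 2.3: Cohort B has 165 per arm, rates 4.1 and 1.6 (difference 2.5 %/year); Cohort A has 75 per arm, rates 7.2 and 3.5 (difference 3.7); SD 8; two-sided 0.05. SAP 4.4.2: visits at Weeks 1, 4, 12, 24, 36, 44 and 52.

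**Planned power reproduced.** Power ≈ Φ(d / (SD × √(2/n)) − 1.96).

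- Cohort A: 3.7 / (8 × √(2/75)) = 3.7 / 1.306 = 2.83; Φ(0.87) = 80.9%.
- Cohort B: 2.5 / (8 × √(2/165)) = 2.5 / 0.881 = 2.84; Φ(0.88) = 81.0%.

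Both agree with the stated figure of about 80%.

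**Simulation.** The documents give no dropout rate, dropout timing or residual SD. Assumed: 10, 20 or 30% leave in both arms, with monotone missingness and the last visit drawn uniformly from Weeks 1, 4, 12, 24, 36, 44 or from Weeks 24, 36, 44; baseline mean 70; intercept SD 8; residual SD 3; true slope SD set so that the fitted per-patient slope SD is 8. There were 1,000 trials per cell with 10 imputations each, combined by Rubin's rules. Estimates are shifts measured against the same trial's complete data.

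Cohort B, planned difference 2.5 %/year:

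| Exits | Dropout | Both arms, with treatment | Placebo only | Reduction, % of 2.5 | Nominal p<0.05, both arms / placebo only |
|---|---|---|---|---|---|
| Weeks 24 to 44 | 10% | 2.50 | 2.44 | 2 | 79% / 77% |
| Weeks 24 to 44 | 20% | 2.50 | 2.38 | 5 | 78% / 75% |
| Weeks 24 to 44 | 30% | 2.49 | 2.32 | 7 | 77% / 74% |
| Weeks 1 to 44 | 10% | 2.51 | 2.36 | 6 | 77% / 73% |
| Weeks 1 to 44 | 20% | 2.48 | 2.20 | 11 | 74% / 65% |
| Weeks 1 to 44 | 30% | 2.52 | 2.08 | 18 | 69% / 58% |

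For example, (2.52 − 2.08) / 2.5 = 18%. The Monte Carlo SE of the gap is at most 0.010. Under the SAP's random slope form, with variance components fixed at their true values, the reductions agree to within 0.1 percentage point. The both-arms version matches the primary observed-case estimate to within 0.01 in every Cohort B cell (2.529 against 2.525 at 30%, Weeks 1 to 44).

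**Range.** With residual SD from 2 to 4 and 10 to 30% dropout, the reduction runs from 1 to 10% (Weeks 24 to 44) and from 5 to 20% (Weeks 1 to 44). At 5% dropout it is 1% or 3%. Cohort A at its planned 3.7 gives 2/4/6% and 6/12/17%. With equal slopes in Cohort A, the two versions differ by at most 0.02 %/year.

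**Second simulation, different assumptions.** Here dropout depends on the last observed change, the intercept SD is 12 and the random-slope SD is 7.46. Cohort B at 10/20/30% missing gives 2.53/2.49/2.51 (both arms) against 2.39/2.25/2.14 (placebo only). The gap at 30% is (2.51 − 2.14) / 2.5 = 15%. At 165 per arm, the share significant is 77% against 65% at 30% missing.

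**The case against.** The strongest reply is that the lead sentence is part of item C and names the source of the imputations. Nothing in the item tells a programmer to fit both arms. If the lead sentence governs, step b merely carries a redundant constant, or lists treatment because that variable selects the placebo patients, and the intended analysis results. This reading is possible, and the missing-at-random result arises only if both arms are fitted. But neither step says so, and the steps are what gets coded. Two programmers could each claim to follow the plan and obtain different answers.

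Second, the effect may be small. Data after stopping study drug are kept (SAP 4.4), and patients who stop are asked to complete assessments (protocol 4.6.1.1), so 30% dropout may be too high, and so may the share of early exits in the Weeks 1 to 44 case. With late exits the gaps are 0.06, 0.12 and 0.17 %/year, or 0.07 to 0.19 of the planned standard error of 0.88. This stands, and the late-exit figures may be the more realistic ones.

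Third, no decision rests on C. It has no success criterion and lies outside the fixed testing sequence, so its nominal p-values carry little weight. This also stands. It limits how serious the point is, but does not settle which analysis is to be run.

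Fourth, the simulations use monotone dropout only, so they say nothing about the size of any effect through step a.

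**Conclusion.** Item C contradicts itself, and no other section resolves it. The conflict and the rank result need no assumption about dropout. The size does: in Cohort B, at 10 to 30% assumed dropout and residual SD 3, the placebo-only estimate is smaller by 2 to 7% of the planned effect with exits at Weeks 24 to 44, and by 6 to 18% with exits over Weeks 1 to 44. The both-arms version reproduces the primary estimate. The primary analysis, the sample size and the type I error plan are untouched. What is at risk is the credibility of one sensitivity analysis, the only one that tests the slope against departures from missing at random in living dropouts. For step a, the gap is one of missing detail. Cohort A matters little in practice, since protocol 1.4 reports no clinically meaningful lung-function difference there.

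**What to change.** Before Cohort B is unblinded, replace the model sentence in step b with wording to this effect: *for each visit, the regression is fitted to placebo patients only, with baseline lung function and all prior visits as predictors, and is applied to missing values in both arms.* Remove treatment group from the predictors.

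Removing the term alone is not enough, because the fitting population would still be unstated. In the second simulation, a pooled fit without treatment happened to give a similar difference (2.39/2.24/2.14), but it imputes from both arms, which is not what the lead sentence says.

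In step a, state which patients inform the MCMC fill of intermittent gaps, and reconcile that with the lead sentence. Keep the 100 imputations, the seeds and Rubin's rules.

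For Cohort A, state in the report which version was run; no rerun is needed. SAP Version 2 describes itself as amended before Cohort B unblinding. If that unblinding has since taken place, state which version was run for Cohort B as well.

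The cost is two SAP sentences, one programming option and one reporting statement, with no new data. The sensitivity estimate will be somewhat less favourable, by the amounts given above.
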